3.1. Analysis Sets

Analysis sets define the participants to be included in an analysis. Analysis sets and their definitions are provided in this section. The analysis set will be identified and included as a subtitle of each table, figure, and listing.

For each analysis set, the number and percentage of participants eligible for inclusion as well as the number and percentage of participants who were excluded and the reasons for their exclusion, will be summarized by cohort, and treatment group if applicable.

A listing of reasons for exclusion from analysis sets will be provided by participant.

3.1.1. All Enrolled Analysis Set

The All Enrolled Analysis Set includes all participants in Cohort 1 who received a study participant identification number in the study after screening, or all participants in Cohort 2 who were randomized in the study.

3.1.2. All Randomized Analysis Set

The All Randomized Analysis Set includes all participants in Cohort 2 who were randomized in the study.

3.1.3. Full Analysis Set

The Full Analysis Set (FAS) includes all enrolled participants in Cohort 1, or all randomized participants in Cohort 2 who received at least 1 dose of study drug. This is the primary analysis set for efficacy analyses.

3.1.4. Safety Analysis Set

The Safety Analysis Set includes all participants who received at least 1 dose of study drug. This is the primary analysis set for safety analyses.

3.1.5. Follow-Up (FU) Analysis Set

The FU Analysis Set includes all participants who have at least 1 follow-up visit, after completing or premature discontinued from the study drugs.

3.1.6. SLGN Pharmacokinetic Analysis Set

The SLGN Pharmacokinetic (PK) Analysis Set will include all enrolled participants who took at least 1 dose of SLGN and have at least 1 nonmissing SLGN concentration value reported by the PK laboratory. This is the primary analysis set for PK analyses associated with SLGN.

3.1.7. SLGN Pharmacokinetic (PK) Substudy Analysis Set

The SLGN PK Substudy Analysis Set will include all enrolled participants who took at least 1 dose of SLGN, participated in the PK substudy, and have at least 1 nonmissing postdose SLGN concentration. This is the primary analysis set for detailed PK analysis of intensive PK sampling associated with SLGN.

3.2. Participant Grouping

For analyses based on the FAS, participants will be grouped according to the treatment group to which they were enrolled for Cohort 1 or to which they were randomized for Cohort 2. For analyses based on the Safety Analysis Set, participants will be grouped according to the actual treatment received. The actual treatment received will differ from the enrolled/randomized treatment group only when their actual treatment differs from enrolled/randomized treatment for the entire treatment duration.

For the PK Analysis Set, participants will be grouped according to the actual treatment they received.

3.3. Strata and Covariates

Cohort 2 participants will be randomized to treatment groups via the interactive voice or web response system (IXRS) in a 2:1 ratio using a stratified randomization schedule. Stratification will be based on the following variable:

• HBsAg $> 3 \log_{10} IU/mL$ or HBsAg $\leq 3 \log_{10} IU/mL$

If there are discrepancies in stratification factor values between the IXRS and the clinical database, the values recorded in the clinical database will be used for analyses. However, in the case that stratification factor data is missing in clinical database, values recorded in the IXRS will be used. Additionally, stratification discrepancies will be reviewed and assessed. Based on the assessment of stratification discrepancies, a sensitivity analysis of the primary endpoint may be performed.

Demographics, baseline characteristics, participants disposition and enrollment, and efficacy endpoints will be evaluated by baseline HBsAg status (HBsAg > or $\leq 3 \log_{10} IU/mL$).

3.4. Examination of Participant Subgroups

There are no prespecified participant subgroupings for efficacy and safety analyses.

3.5. Multiple Comparisons

Adjustments for multiplicity will not be made, because no formal statistical testing will be performed in this study.

3.6. Missing Data and Outliers

3.6.1. Missing Data

In general, missing data will not be imputed unless methods for handling missing data are specified. Exceptions are presented in this document.

For missing last dosing date of study drug, imputation rules are described in Section 4.2. The handling of missing or incomplete dates for AE onset is described in Section 7.1.6.4, and for prior HBV and concomitant medications in Section 7.4.

3.6.2. Outliers

Outliers of non-PK data will be identified during the data management and data analysis process, but no sensitivity analyses will be conducted. All data will be included in the data analysis.

3.7. Data Handling Conventions and Transformations

The following conventions will be used for the imputation of date of birth when it is partially missing or not collected:

- If only month and year of birth is collected, then "15" will be imputed as the day of birth
- If only year of birth is collected, then "01 July" will be imputed as the day and month of birth
- If year of birth is missing, then date of birth will not be imputed.

In general, age collected at Day 1 (in years) will be used for analyses and presented in listings. If age at Day 1 is not available for a participant, then age derived based on date of birth and the Day 1 visit date will be used instead. If an enrolled participant was not dosed with any study drug, the enrollment date for Cohort 1 or randomization date for Cohort 2 will be used instead of the Day 1 visit date. For screen failures, the date the first informed consent was signed will be used for the age derivation. Age required for longitudinal and temporal calculations and analyses (e.g., estimates of creatinine clearance, age at date of AE) will be based on age, and derived from date of birth and the date of the measurement or event, unless otherwise specified.

Non-PK data that are continuous in nature but are less than the lower limit of quantitation (LOQ) or above the upper LOQ will be imputed as follows:

- A value that is 1 unit less than the lower LOQ at the same precision level of the originally reported value will be used to calculate descriptive statistics if the datum is reported in the form of "< x" (where x is considered the lower LOQ). For example, if the values are reported as < 50 and < 5.0, values of 49 and 4.9, respectively, will be used to calculate summary statistics. An exception to this rule is any value reported as < 1 or < 0.1, etc. For values reported as < 1 or < 0.1, a value of 0.9 or 0.09, respectively, will be used to calculate summary statistics.
- A value that is 1 unit above the upper LOQ will be used to calculate descriptive statistics if the datum is reported in the form of "> x" (where x is considered the upper LOQ). Values with decimal points will follow the same logic as above.
- The lower or upper LOQ will be used to calculate descriptive statistics if the datum is reported in the form of " \leq x" or " \geq x" (where x is considered the lower or upper LOQ, respectively).

If methods based on the assumption that the data are normally distributed are not adequate, analyses may be performed on transformed data (eg, log₁₀ transformation may be used for quantitative HBsAg, HBV DNA, HBeAg if applicable, HBV RNA, and HBcrAg) or nonparametric analysis methods may be used, as appropriate.

Sparse PK concentration values that are below the limit of quantitation (BLQ) will be presented as "BLQ" in the data listing.

Natural logarithm transformation will be used for analyzing non-BLQ concentrations and PK parameters in intensive PK samples. Concentration values that are BLQ will be presented as "BLQ" in the concentration data listing. Values that are BLQ will be treated as 0 at predose and postdose time points for summary purposes. The number of samples will be summarized to reflect the actual number of samples assessed at that time point.

At predose, if all concentration values are BLQ, then the mean, and order statistics (minimum, Q1, median, Q3, and maximum) will be displayed as 0 and the rest of the summary statistics (ie, SD and CV) will be missing. If any values are non-BLQ, then the number of samples, order statistics, and all summary statistics will be displayed.

At any given postdose time point, if more than one-third of the participants have a concentration value of BLQ, then only the number of samples and order statistics will be displayed; otherwise, order statistics and summary statistics will be displayed.

The following conventions will be used for the presentation of order statistics for postdose time points:

- If at least 1 participant has a concentration value of BLQ for the time point, the minimum value will be displayed as "BLO."
- If more than 25% of the participants have a concentration data value of BLQ for a given time point, the minimum and Q1 values will be displayed as "BLQ."
- If more than 50% of the participants have a concentration data value of BLQ for a given time point, the minimum, Q1, and median values will be displayed as "BLQ."
- If more than 75% of the participants have a concentration data value of BLQ for a given time point, the minimum, Q1, median, and Q3 values will be displayed as "BLQ."
- If all participants have concentration data values of BLQ for a given time point, all order statistics (minimum, Q1, median, Q3, and maximum) will be displayed as "BLQ."

Concentration related PK parameters (eg, C_{last} , C_{max} , and C_{tau}) that are BLQ will be excluded before log transformation or statistical model fitting and displayed as described above.

3.8. Analysis Visit Windows

3.8.1. Definition of Study Day

Study day will be calculated from the first dosing date of any study drug and derived as follows:

- For postdose study days: Assessment Date First Dosing Date + 1
- For days prior to the first dose: Assessment Date First Dosing Date

Therefore, Study Day 1 is the day of first dose of any study drug administration.

The last dose date of the study drug will be the stop date on the study drug administration eCRF for the record where the "study drug was permanently withdrawn" flag is "Yes".

3.8.2. Analysis Visit Windows

Participant visits might not occur on protocol-specified days. Therefore, for the purpose of analysis, observations will be assigned to analysis windows as specified in Table 3-1 to Table 3-12.

Data collected up to the last on-treatment date + 3 days will be considered as on-treatment data, whereas data collected afterwards will be considered as follow-up data.

For each drug, the last on-treatment date is defined as follows:

- Last on-treatment date for VIR-2218 = (last injection date of VIR-2218 + 28 days) -1
- Last on-treatment date for nivolumab = (last injection date of nivolumab + 28 days) 1
- Last on-treatment date for selgantolimod = (last dose date of selgantolimod + 7 days) -1

For Cohort 1 and Cohort 2 Group A, the composite last on-treatment date is the latest date of the last on-treatment date of VIR-2218, nivolumab, or SLGN.

For Cohort 2 Group B, the composite last on-treatment date is the latest date of the last on-treatment date of nivolumab or SLGN.

Participants are allowed to continue taking TAF after the discontinuation of study treatments, hence TAF will not be considered for constructing the analysis windows.

The follow-up day (FU Day) in Posttreatment tables is defined as:

• FU Day = Assessment date – composite last on-treatment date.

A baseline value is defined as the last available value collected on or prior to the date of first dose of any study drug. An unscheduled visit prior to the first dosing of study drug will be included in the calculation of the baseline value, if applicable.

The analysis windows for on-treatment assessments are provided in Table 3-1 to Table 3-9. Table 3-10 to Table 3-12 provide analysis windows for posttreatment assessments.

Table 3-1. Cohort 1 and Cohort 2 Group A: Analysis Visit Windows for On-treatment Vital Signs, Hematology, Chemistry, Coagulation, Quantitative Plasma HBV DNA, Quantitative HBV (serum HBsAg, HBcrAg, HBeAg, and HBV RNA), Qualitative HBV Serology (HBeAg, hepatitis B e antibody (HBeAb), HBsAg, and hepatitis B surface antibody (HBsAb))

		Visit Window Study Day	
Visit	Study Day	Lower Limit	Upper Limit
Baseline	1	(none)	1
Week 4	29	2	43
Week 8	57	44	71
Week 12	85	72	92
Week 14	99	93	106
Week 16	113	107	127
Week 20	141	128	155
Week 24	169	156	183
Week 28	197	184	211
Week 32	225	212	239
Week 36	253	240	≥ 253

Table 3-2. Cohort 1 and Cohort 2 Group A: Analysis Visit Windows for On-treatment Urinalysis

		Visit Windo	w Study Day
Visit	Study Day	Lower Limit	Upper Limit
Baseline	1	(none)	1
Week 4	29	2	43
Week 8	57	44	71
Week 12	85	72	99
Week 16	113	100	127
Week 20	141	128	155
Week 24	169	156	183
Week 28	197	184	211
Week 32	225	212	239
Week 36	253	240	≥ 253

Table 3-3. Cohort 1 and Cohort 2 Group A: Analysis Visit Windows for On-treatment Body Weight

		Visit Window Study Day	
Visit	Study Day	Lower Limit	Upper Limit
Baseline	1	(none)	1
Week 12	85	2	99
Week 16	113	100	127
Week 20	141	128	155
Week 24	169	156	183
Week 28	197	184	211
Week 32	225	212	239
Week 36	253	240	≥ 253

Table 3-4. Cohort 1 and Cohort 2 Group A: Analysis Visit Windows for On-treatment APRI, FibroTest, ECG, and Estimated Creatinine Clearance (using the Cockcroft-Gault method)

		Visit Window Study Day	
Visit	Study Day	Lower Limit	Upper Limit
Baseline	1	(none)	1
Week 12	85	2	169
Week 36	253	170	≥ 253

Table 3-5. Cohort 1 and Cohort 2 Group A: Analysis Visit Windows for On-treatment Ophthalmologic Examination

		Visit Window Study Day	
Visit	Study Day	Lower Limit	Upper Limit
Baseline	1	(none)	1
Week 24	169	2	211
Week 36	253	212	≥ 253

Table 3-6. Cohort 2 Group B: Analysis Visit Windows for On-treatment Hematology, Chemistry, Coagulation, Quantitative Plasma HBV DNA, Quantitative HBV (serum HBsAg, HBcrAg, HBeAg, and HBV RNA), Qualitative HBV Serology (HBeAg, HBeAb, HBsAg, and HBsAb)

		Visit Window Study Day	
Visit	Study Day	Lower Limit	Upper Limit
Baseline	1	(none)	1
Week 4	29	2	43
Week 8	57	44	71
Week 12	85	72	92
Week 14	99	93	106
Week 16	113	107	127
Week 20	141	128	155
Week 24	169	156	≥ 169

Table 3-7. Cohort 2 Group B: Analysis Visit Windows for On-treatment Vital Signs

		Visit Window	w Study Day
Visit	Study Day	Lower Limit	Upper Limit
Baseline	1	(none)	1
Week 2	15	2	22
Week 4	29	23	43
Week 8	57	44	71
Week 12	85	72	92
Week 14	99	93	106
Week 16	113	107	127
Week 20	141	128	155
Week 24	169	156	≥ 169

Table 3-8. Cohort 2 Group B: Analysis Visit Windows for On-treatment Urinalysis, and Body Weight

		Visit Window Study Day	
Visit	Study Day	Lower Limit	Upper Limit
Baseline	1	(none)	1
Week 4	29	2	43
Week 8	57	44	71
Week 12	85	72	99
Week 16	113	100	127
Week 20	141	128	155
Week 24	169	156	≥ 169

Table 3-9. Cohort 2 Group B: Analysis Visit Windows for On-treatment APRI, FibroTest, ECG, Estimated Creatinine Clearance (using the Cockcroft-Gault method), and Ophthalmologic Examination

		Visit Window Study Day	
Visit	Study Day	Lower Limit	Upper Limit
Baseline	1	(none)	1
Week 12	85	2	127
Week 24	169	128	≥ 169

Table 3-10. Cohort 1, Cohort 2 Groups A and B: Analysis Visit Windows for Posttreatment Hematology, Chemistry, Coagulation, Quantitative Plasma HBV DNA, HBV genotyping, Quantitative HBV Serology (HBsAg, HBcrAg, HBeAg, and HBV RNA), Qualitative HBV Serology (HBeAg, HBeAb, HBsAg, and HBsAb) and Vital Signs

		Visit Window FU Day	
Visit	FU Day	Lower Limit	Upper Limit
FU Week 2*	15	4	22
FU Week 4	29	23	43
FU Week 8	57	44	71
FU Week 12	85	72	127
FU Week 24	169	128	211
FU Week 36	253	212	295
FU Week 48	337	296	≥ 337

^{*} FU Week 2 was defined in protocol amendment 1, but was removed from protocol amendment 2. Since a substantial amount of participants have already completed FU Week 2 per protocol amendment 1, this visit will be kept in analysis.

Table 3-11. Cohort 2 Groups A and B: Analysis Visit Windows for Posttreatment APRI and FibroTest

		Visit Window FU Day	
Visit	FU Day	Lower Limit	Upper Limit
FU Week 12	85	4	211
FU Week 48	337	212	≥ 337

Table 3-12. Cohort 1, Cohort 2 Groups A and B: Analysis Visit Windows for Posttreatment Body Weight, ECG, Estimated Creatinine Clearance (using the Cockcroft-Gault method)

		Visit Window FU Day	
Visit	FU Day	Lower Limit	Upper Limit
FU Week 48	337	4	≥ 337

3.8.3. Selection of Data in the Event of Multiple Records in an Analysis Visit Window

Depending on the statistical analysis method, single values may be required for each analysis window. For example, change from baseline by visit usually requires a single value, whereas a time-to-event analysis would not require 1 value per analysis window.

If multiple valid, nonmissing, continuous measurements exist in an analysis window, records will be chosen based on the following rules if a single value is needed:

- For baseline, the last nonmissing value on or prior to the first dosing date of study drug will be selected, unless specified differently. If multiple measurements occur on the same day, the last nonmissing value prior to the time of first dosing of study drug will be considered as the baseline value. If there are multiple records with the same time or no time recorded on the same day, the baseline value will be the average of these measurements.
- For postbaseline values (except for alanine aminotransferase [ALT]):
 - The record closest to the nominal day for that visit will be selected.
 - If there are 2 records that are equidistant from the nominal day, the later record will be selected.
 - If there is more than 1 record on the selected day, the average will be taken except for qHBsAg (IU/mL), HBV DNA (IU/mL), and quantitative HBeAg (IU/mL), for which the geometric mean will be taken.

• For postbaseline ALT values:

- The record with the largest value within the same analysis window will be selected.
- If there is more than 1 record with the largest value, the latest record will be selected.
- If there are multiple largest records with the same time or no time recorded on the same day, any one of these measurements can be selected as the analysis value.

If multiple valid, nonmissing, categorical measurements exist in an analysis window, and a single value is needed, records will be chosen based on the following rules:

• For baseline, the last available record on or prior to the date of the first dose of study drug will be selected. If there are multiple records with the same time or no time recorded on the same day, the value with the lowest severity will be selected for safety data (eg, normal will be selected over abnormal for safety electrocardiogram [ECG] findings), and the most conservative value will be selected for efficacy data (eg, negative will be selected over positive for HBeAg and HBsAg, whereas positive will be selected over negative for HBeAb and HBsAb).

• For postbaseline values:

- The most conservative value (eg, abnormal will be selected over normal for safety ECG) within the analysis window will be selected, except for HBV serology (HBsAg, HBsAb, HBeAg, and HBeAb), for which the most favorable value (ie, negative will be selected over positive for HBsAg and HBeAg, whereas positive will be selected over negative for HBsAb and HBeAb) will be selected.
- In the event that more than 1 value within an analysis window are equal, the value collected closest to the nominal day will be selected.
- If there are 2 records that are equidistant from the nominal day, the later record will be selected.
- If there is more than 1 record on the selected day, the latest record will be selected; if these measurements were recorded at the same time or no time recorded, any one of these measurements can be selected as the analysis value.

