7.6. Other Safety Measures

For Cohort 1 and Cohort 2 Group A, ophthalmic examinations will be performed at Screening, Week 24, and Week 36. For Cohort 2 Group B, ophthalmic examinations will be performed at Screening, Week 12, and Week 24.

A shift table of the overall assessment of ophthalmology results at each visit compared with baseline values will be presented for each cohort (and for each treatment group for Cohort 2) using the following categories: normal; abnormal, not clinically significant; abnormal, clinically significant; or missing/unknown. The number and percentage of participants in each cross-classification group of the shift table will be presented. Participants with a missing value at baseline or postbaseline will not be included in the denominator for percentage calculation. No formal statistical testing is planned.

By-participant listings for ophthalmology assessment results will be provided by participant ID number and visit in chronological order.

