- e The ED visit should be performed within 14 days from notification of study discontinuation.
- f Obtain written informed consent, including Main Informed Consent, CCI
- g Record any SAEs and all AEs related to protocol mandated procedures occurring after signing of the consent form. After drug administration, report all AEs and SAEs.
- h Participants must rest quietly in the supine position for a minimum of 5 minutes prior to the recording.
- i At ED visit, these procedures are optional and to be done as needed.
- j Ophthalmologic examination at screening should be performed during the screening window, ie, within 45 days of randomization. Ophthalmologic examinations post-Day 1
- k should occur within -4 to +10 days of visit.
- 1 FibroScan testing where applicable for liver disease staging.
- m In the event of a positive result for serology and/or antigen testing for HIV, HDV, or HCV, reflex tests will be performed as necessary.
- n Cohort 2 Group A biomarker collection. Collect pre-SLGN dose administration at Baseline/Day 1, Week 12, 4 hours and 24-72 hours postdose. Collect at Week 14, predose.
- o Collect pre-SLGN dose administration at Week 32, 4 hours and 24-72 hours postdose.
- p Cohort 2 Group B biomarker collection. Collect pre-SLGN dose administration on Baseline/Day 1, 4 hours and 24-72 hours postdose. Collect at Week 2, pre-dose. Collect pre-SLGN dose administration at Week 20, 4 hours and 24-72 hours postdose.
- q The sparse PK collection for VIR-2218 at baseline/Day 1 should occur predose and postdose. Postdose sparse PK collection for VIR-2218 should occur any time between 1 and 5 hours postdose relative to VIR-2218 administration.
- r Sparse PK collection for SLGN should occur any time between 1 and 5 hours postdose relative to SLGN administration. The collection at Baseline/Day 1 is only applicable to Cohort 2 Group B. The collection at Week 32 is only applicable to Cohort 2 Group A.

CCI

- x For Group A, intensive PK sample to be drawn at any one visit at Week 20, 24, 28 or 32 **relative to SLGN** dosing in clinic on the morning of the intensive PK visit. For Group B, sample will be collected Week 12 or later **relative to SLGN** dosing in clinic on the morning of the intensive PK visit.
- y Group A and B: Collection will occur at Predose, 0.25, 0.5, 1, 1.5, 2, 3, 4, 5, 8, 10, 12 and 24 hours postdose CCI

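### The +3-day on-treatment cut-off leaves some permitted end-of-treatment eye examinations without an analysis visit, because ophthalmology has no post-treatment window

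*SAP*

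**What the plan says.** Section 3.8.2 sets one boundary for all assessments: "Data collected up to the last on-treatment date + 3 days will be considered as on-treatment data, whereas data collected afterwards" are follow-up data. The boundary is counted from a composite date. The rule covering Cohort 1 together with Group A reads: "the composite last on-treatment date is the latest date of the last on-treatment date of VIR-2218, nivolumab, or SLGN". The Group B rule leaves out VIR-2218 and reads: "the composite last on-treatment date is the latest date of the last on-treatment date of nivolumab or SLGN". The component dates include "Last on-treatment date for selgantolimod = (last dose date of selgantolimod + 7 days) -1" and "Last on-treatment date for VIR-2218 = (last injection date of VIR-2218 + 28 days) -1"; nivolumab follows the same 28-day rule as VIR-2218.

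The ophthalmologic examination is windowed in Table 3-5 (Cohort 1 and Group A) and Table 3-9 (Group B), both headed as on-treatment. The post-treatment windows are Tables 3-10 to 3-12. Table 3-12, for example, covers "Analysis Visit Windows for Posttreatment Body Weight, ECG, Estimated Creatinine Clearance". None of the three includes ophthalmology.

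The footnotes to both schedules in Appendix 1 give eye examinations after Day 1 their own tolerance; for Cohort 2, they "should occur within -4 to +10 days of visit". The end-of-treatment visit itself carries a window of -5 days.

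Section 7.6 schedules full examinations at screening and Weeks 24 and 36 (Group B: screening and Weeks 12 and 24). "A shift table of the overall assessment of ophthalmology results at each visit compared with baseline values will be presented" by cohort and group. Participants with a missing baseline or postbaseline value leave the percentage denominator.

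**The concern.** The 3-day allowance is shorter than the 10 days that the schedule grants this one examination. For laboratory tests, vital signs, weight and ECG, a record past the cut-off moves into a post-treatment window. An eye examination past the cut-off has nowhere to go. Since Section 7.6 works by visit, a result without an analysis visit cannot be tabulated.

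At stake is the last scheduled full eye examination, at the end of exposure. An examination that was done, within its permitted time, would be omitted or would look the same as one never done. The same SAP treats adverse events and laboratory abnormalities as treatment-emergent up to 30 days after the composite date (Sections 7.1.6.1 and 7.2.2.1). The affected examinations fall well inside that period.

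**Working it through.** **Inputs.** Weekly SLGN, 24 doses, starting at Week 12 (Day 85) in Cohort 1 and Group A and on Day 1 in Group B (Section 1.2). Last VIR-2218 injection at Week 20, Day 141. Nivolumab, if fully dosed, last given at Week 32, Day 225 (Group B: Week 20, Day 141). Nominal end-of-treatment days are 253 and 169 (Tables 3-5 and 3-9). Examination tolerance is -4 to +10 days, which is 15 days.

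**Composite date and cut-off, on-schedule dosing**

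- Cohort 1 and Group A: last SLGN dose 85 + 23 × 7 = Day 246, so its last on-treatment date is 246 + 7 - 1 = Day 252. VIR-2218: 141 + 28 - 1 = Day 168. Nivolumab, if fully dosed: 225 + 28 - 1 = Day 252. Composite Day 252, cut-off 252 + 3 = Day 255. Stopping nivolumab does not change this, because SLGN alone gives Day 252.
- Group B as planned: last SLGN dose 1 + 23 × 7 = Day 162, giving 162 + 7 - 1 = Day 168. Nivolumab: 141 + 28 - 1 = Day 168. Composite Day 168, cut-off Day 171.

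**Check against the SAP.** Day 256 - 252 = FU Day 4, which is the lowest limit in each of Tables 3-10 to 3-12. The reading of the cut-off therefore matches the plan's own tables.

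**Permitted days outside every window.** Last permitted day minus cut-off = (visit day + 10) - (composite + 3).

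| Case | Cohort 1 and Group A | Group B as planned | Days of 15 |
|---|---|---|---|
| Visit on nominal day, dosing on schedule | 263 - 255 | 179 - 171 | 8 |
| Visit 5 days early, dosing on schedule | 258 - 255 | 174 - 171 | 3 |
| Visit on nominal day, composite date 2 days later (last dose late) | 263 - 257 | 179 - 173 | 6 |
| Visit on nominal day, composite date 2 days earlier (last dose early) | 263 - 253 | 179 - 169 | 10 |

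In the first case the affected days are 256-263 (Group B: 172-179), that is FU Days 4 to 11. In the last case the latest permitted examination is at 263 - 250 = FU Day 13. The 2-day dose shift is an assumption, chosen to match the ± 2 days allowed for most treatment visits. The ranges move one input at a time.

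**The case against.** *The open upper limits (≥ 253 and ≥ 169) could take in late examinations.* Both tables are for on-treatment data, and the 3-day rule has already classed these records as follow-up. If the open limit was meant to override the rule, the SAP does not say so, and the text needs settling either way.

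*The results are not lost to the report.* This stands. Section 7.6 requires by-participant listings of all ophthalmology results. A reader might also infer that the shift table hides the loss. It need not: the table has a missing/unknown category, so the count may be visible, though not as an examination that was done.

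*Uveitis is covered elsewhere.* This also stands. Section 7.1.9 analyses potential uveitis from adverse events, independently of the visit windows. An examination finding reported as an adverse event is counted there. What is affected is the systematic assessment in the shift table.

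*The symptom-directed examinations in follow-up have no window either.* A reader might call that a further gap. Appendix 1 lists them separately from the full examination, Section 7.6 names only the full examinations, and no full examination is scheduled in follow-up. The documents do not require a window for them.

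*Group B must be hit hardest, because its treatment was stopped early.* This is tempting but not supported. An early stop moves the composite date, but that date can still run to 27 days after the last nivolumab dose, and the SAP gives no actual dates. A closing examination could fall on either side of the cut-off.

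**Conclusion.** The gap is real and narrow. Followed as written, Section 3.8.2 excludes some compliant end-of-treatment eye examinations from one descriptive safety table. With on-schedule dosing, 3 to 8 of the 15 permitted days have no window; with a nominal-day visit and the last dose 2 days late or early, 6 to 10.

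These are calendar days, not examinations. Eight of 15 is the top of the on-schedule range, not the expected loss. An examination done on the end-of-treatment visit day loses nothing in the on-schedule cases (Day 253 is before the cut-off of Day 255; Group B, Day 169 before Day 171). The number affected cannot be derived from the document. The Group B figures describe the planned 24-week course, not the early stop described in Section 1.2.1. No efficacy result and no adverse event analysis depends on this point.

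**What to change.** Add one sentence to Section 3.8.2, for ophthalmologic examinations only: records up to the composite last on-treatment date + 14 days count as on-treatment, and are then assigned to visits by the existing study-day limits in Tables 3-5 and 3-9. Fourteen days covers composite + 11 (on-schedule dosing) and composite + 13 (last dose 2 days early).

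Keeping the study-day limits matters. Moving every late record straight into Week 36 or Week 24 would mislabel early discontinuers, whose closing examination may belong to the Week 24 window (Days 2-211, Table 3-5) or the Week 12 window (Days 2-127, Table 3-9). Table 3-9 also serves APRI, FibroTest, ECG and creatinine clearance. Those have post-treatment windows from FU Day 4 and should stay under the 3-day rule.

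A worst-postbaseline row in the shift table is optional.

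Cost: a short text change and a programming rule, with no new data. Downside: a few examinations counted as on-treatment will fall up to two weeks after the composite date. Because the SAP is already signed, the change would be recorded as a SAP revision or, as Section 1 provides, in the CSR.
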